3.3. Other Endpoint(s)

[figure not shown]
3.3.1. Cumulative Rate of Excretion (Period 1)

See [Section 3.1.1](#).

3.3.2. Pharmacokinetics Parameters (Oral Unlabeled PF-07081532 - Period 2)

See [Section 3.2.1](#).

CCI

3.4. Baseline Variables

Not applicable.

3.5. Safety Endpoints

Assessment of treatment emergent AEs, clinical laboratory abnormalities, vital signs, ECG parameters.

An adverse event is considered treatment emergent (TEAE) relative to a given treatment if:

- the event starts during the effective duration of treatment (i.e. starting on or after the dose of PF-07081532 but before this dose plus lag time)

The effective duration of treatment is determined by the lag time. Any event occurring within the lag time is attributed to the corresponding treatment. The lag time is defined by the Pfizer Standard of 365 days post last dose of IP.

Events that occur in a non-treatment period (for example, Washout or Follow-up) will be counted as treatment emergent and attributed to the most recent treatment taken.

A 3-tier approach for summarizing AEs will not be used due to the low number of participants planned to be recruited.

The following data are considered in standard safety summaries (see protocol for collection days and list of parameters):

- adverse events,
- laboratory data,
- vital signs data,
- ECG results.

For laboratory, vital signs and ECG data, the baseline measurement is the planned last pre-dose measurement taken on Day -1 or Day 1 (as applicable) in each period.

4. ANALYSIS SETS (POPULATIONS FOR ANALYSIS)

Data for all participants will be assessed to determine if participants meet the criteria for inclusion in each analysis population prior to unblinding and releasing the database and classifications will be documented per standard operating procedures.

For purposes of analysis, the following analysis sets are defined:

Participant Analysis Set	Description
Enrolled	“Enrolled” means a participant’s, or their legally authorized representative’s, agreement to participate in a clinical study following completion of the informed consent process and assignment to and dosing with study intervention. A participant will be considered enrolled if the informed consent is not withdrawn prior to participating in any study activity after screening. Potential participants who are screened for the purpose of determining eligibility for the study, but do not participate in the study, are not considered enrolled, unless otherwise specified by the protocol.

Participant Analysis Set	Description
Safety analysis set	All participants assigned to study intervention and who take at least 1 dose of study intervention.
Extent of excretion analysis set	In Period 1, extent of excretion population will be defined by evaluable participants who have received 1 dose of [¹⁴C]PF-07081532 and who have complete total radioactivity concentration (urinary and fecal) data and who had no protocol deviations that may have affected the extent of excretion analysis.
PK concentration set	
The PK concentration population for PF-07081532 is defined as all participants dosed with PF-07081532 or [¹⁴C]PF-07081532, who have at least one PF-07081532 concentration.
 
The PK concentration population for [¹⁴C]PF-07081532 is defined as all participants dosed with [¹⁴C]PF-07081532, who have at least one [¹⁴C]PF-07081532 measurement.
 
The PK concentration population for total [¹⁴C] is defined as all participants dosed with [¹⁴C]PF-07081532, who have at least one total [¹⁴C] measurement.

PK parameter set	
The PK parameter analysis population for PF-07081532 is defined as all participants dosed with PF-07081532 or [¹⁴C]PF-07081532 who have at least one of the PF-07081532 PK parameters of interest.
 
The PK parameter analysis population for [¹⁴C]PF-07081532 is defined as all participants dosed with [¹⁴C]PF-07081532 who have at least one of the [¹⁴C]PF-07081532 PK parameters of interest.
 
The PK parameter analysis population for total [¹⁴C] is defined as all participants dosed with [¹⁴C]PF-07081532 who have at least one of the total [¹⁴C] PK parameters of interest.

Urine PK parameter analysis population	
The urine PK parameter analysis population for total radioactivity excreted into urine is defined as all participants dosed who have at least one of the urine [¹⁴C] parameters of interest.

CCI	

5. GENERAL METHODOLOGY AND CONVENTIONS

5.1. Hypotheses and Decision Rules

There is no statistical hypothesis testing planned for this study and no statistical decision rules will be applied.

5.2. General Methods

For all safety outputs produced, the following treatment labels (or similar) will be used:

- [¹⁴C]PF-07081532 30 mg oral
- Unlabeled PF-07081532 30 mg oral & [¹⁴C]PF-07081532 100 µg IV

For all PK outputs produced, the following analyte labels (or similar) related to the above treatments will be used:

- Related to “[¹⁴C]PF-07081532 30 mg oral” treatment from Period 1:
 - PF-07081532 (Period 1)
 - Total (¹⁴C) (Period 1)
- Related to “Unlabeled PF-07081532 30 mg oral & [¹⁴C]PF-07081532 100 µg IV” treatment from Period 2:
 - PF-07081532 (Period 2)
 - [¹⁴C]PF-07081532 (Period 2)

5.2.1. Analyses for Continuous Endpoints

Unless otherwise stated, continuous variables will be presented using summary statistics: number of observations, arithmetic mean, standard deviation, median, minimum and maximum values.

5.2.2. Analyses for Categorical Endpoints

Categorical variables will be presented using summary statistics: number of observations and percentages.

5.2.3. Mixed Model for Continuous Endpoints

A *mixed effect model with treatment as a fixed effect and participant as a random effect* will be used. *Estimates of the adjusted (least squares) mean differences (Test-Reference) and the corresponding 90% confidence interval will be obtained from the model. The adjusted mean differences and 90% confidence intervals for the differences will be exponentiated to provide estimates of the ratio of adjusted geometric means (Test/Reference) and 90% confidence interval for the ratio.*

The mixed effects model will be implemented using SAS Proc Mixed, with REML estimation method and the Kenward-Roger degrees of freedom algorithm.

Example code is shown in Appendix 1.

Residuals from the models will be examined for normality and the presence of outliers via visual inspection of plots of residuals vs predicted values and normal probability plots of residuals but these will not be included in the clinical study report. If there are major deviations from normality or outliers (where studentized residuals are greater than 3 or less than -3) then the effect of these on the conclusions may be investigated through alternative transformations and/or analyses excluding outliers. Justification for any alternative to the planned analysis will be given in the report of the study if applicable.

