2.3. Study Design

C3991006 is a Phase 1, open-label, 2-period, fixed sequence study to characterize the metabolic profile and routes of excretion of oral [^{14}C]PF-07081532 and to evaluate the absolute oral bioavailability (F) and fraction absorbed (F_a) of PF-07081532 in healthy male participants.

Participants will be screened for enrollment in this study within 28 days of dosing on Day 1 of **Period 1**, to confirm that they meet the inclusion/exclusion criteria specified in Section 5 of the protocol. The expected duration of participation from screening to follow-up will be approximately 8 weeks (minimum) to approximately 12 weeks (maximum). The overall study design is summarized in the schema below.

- a. See Section 4.1 of the protocol for details on Period 1 discharge criteria.
- b. At least 21 days of washout is required between dosing in Period 1 and Period 2.
- c. In Period 2, participants will be discharged from the CRU on Day 7.

Regimen in Period 1: An oral dose of 30 mg PF-07081532 containing approximately 250 nCi [¹⁴C] (ie, radiolabeled PF-07081532, [¹⁴C]PF-07081532) will be administered within approximately 10 minutes of completion of a standard breakfast.

Regimen in Period 2: An oral dose of 30 mg unlabeled PF-07081532 will be administered followed at approximate T_{max} by an IV dose of 250 nCi [¹⁴C] in 100 μ g of PF-07081532 (ie, [¹⁴C]PF-07081532). The [¹⁴C]PF-07081532 IV dose will be administered as an infusion over approximately 15 minutes, starting at approximately 1 hour (T_{max}) after the administration of the oral unlabeled PF-07081532 dose. Oral unlabeled PF-07081532 will be administered within approximately 10 minutes of completion of a standard breakfast.

In Period 1, a sufficient number of participants will be admitted on Day -1 to the CRU to ensure that 6 participants are dosed on Day 1. Any participants who are prematurely withdrawn (or offer non-evaluable or partially evaluable data) will be replaced to ensure 6 evaluable participants completing Period 1. In Period 2, participants who are prematurely withdrawn may be replaced at the discretion of sponsor.

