9. APPENDICES

Appendix 1. Example SAS Code for Mixed Model

An example of the PROC MIXED code:

```
proc mixed data=tab.pk;
  class treatment subject;
  model &var = treatment / ddfm=KR;
  random subject /subject=subject;
  lsmeans treatment/ diff cl alpha=0.1;
run;
```

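### Does the outlier cut-off of 3 fail because SAP 5.2.3 does not say how residuals are studentized?

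*SAP*

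**What the plan says.** SAP 5.2.3 specifies a "mixed effect model with treatment as a fixed effect and participant as a random effect", fitted "with REML estimation method and the Kenward-Roger degrees of freedom algorithm". It is applied to log dose-normalized AUC for F (SAP 6.2.2) and to log percent of dose in urine for Fa (SAP 6.2.3). Residuals are inspected in plots against predicted values and in normal probability plots, and these plots stay out of the study report. If there are major departures from normality, or "outliers (where studentized residuals are greater than 3 or less than -3", their effect "may be investigated through alternative transformations and/or analyses excluding outliers". Any alternative to the planned analysis must be justified in the report.

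The example code in SAP Appendix 1 does not settle the residual type. Its two relevant statements are "model &var = treatment / ddfm=KR" and "random subject /subject=subject", with no residual or influence option.

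Two other provisions decide how many values enter the model. SAP 2.3 says "In Period 2, participants who are prematurely withdrawn may be replaced at the discretion of sponsor", and SAP 4 defines the urine population as "all participants dosed who have at least one of the urine" parameters of interest.

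**The concern.** In a dataset of about 12 values, an internally studentized residual has a hard upper limit close to 3. A cut-off of 3 may then be nearly or wholly out of reach, while the same number applied to externally studentized (deleted) residuals works reasonably. One unstated word would decide whether the only numeric outlier rule for F and Fa operates, and two analysts could reach opposite answers on the same data.

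The stake is an undetected aberrant value among six participants. A 3-fold error in one participant's AUC shifts the estimate of F by a factor of 3^(1/6) = 1.20. At an assumed within-participant log-SD of 0.15 it widens the 90% interval (upper limit divided by lower) from a median of about 1.38 to 2.13-2.20.

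**Working it through.** **Inputs.** There are about six participants (Protocol 9.5), so six pairs give N = 12 for each endpoint. Treatment has two levels, so there are p = 2 fixed parameters (SAP 5.2.3 and Appendix 1). The plan states no figure to reproduce here, and it gives no variability.

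**How N can differ from 12.** A participant lost before Period 2 and not replaced contributes nothing to F, because both of its arms are in Period 2; that gives N = 10. His oral urine value can stay in the Fa model, giving N = 11. In the other direction, withdrawn or partly evaluable Period 1 participants are replaced (SAP 2.3). A replaced participant with one urine parameter remains in the urine population, so N = 13 or 14 is also possible.

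**Ceiling, internal reading.** Let V be the fitted covariance of y, R its residual part and P the REML projection matrix. With the scale estimated by REML, y'Py = N - p. The marginal residual is VPy with variance VPV, and the conditional residual is RPy with variance RPR. By Cauchy-Schwarz, in either form,

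(studentized residual)² ≤ N - p.

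With p = 2:

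| N | Ceiling |
|---|---|
| 14 | √12 = 3.46 |
| 13 | √11 = 3.32 |
| 12 | √10 = 3.16 |
| 11 | √9 = 3.00 |
| 10 | √8 = 2.83 |

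No variability assumption is needed. A numerical search with REML fits and planted errors reached 3.1623, 3.0000 and 2.8284 at N = 12, 11 and 10 and never exceeded them.

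**External equivalent.** With the variance ratio held at its full-data estimate, t_ext = t_int × √[(N-3)/(N-2-t_int²)]. Setting t_ext = 3 gives t_int = 3√(N-2)/√(N+6), which is 2.24, 2.18 and 2.12 at N = 12, 11 and 10.

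**Detection with six complete pairs.** These rates come from simulation and assume between-participant log-SD 0.2-0.4 and within-participant log-SD 0.1-0.2.

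| Error in one value | Internal, beyond 3 | External conditional, beyond 3 |
|---|---|---|
| 3-fold | about 0.1-6% | 51-93% |
| 10-fold | 6-69% | not run |
| 100-fold | 64-99.9% | not run |
| none (clean data) | not run at these SDs | about 5-15% |

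At 0.1 for both SDs, the internal rule flags a 3-fold error in 27-28% of datasets. Without a planted error, a separate run of 1,000 datasets per setting gave an internal marginal residual beyond 3 in 0.1% at within-participant correlation 0, and in none at 0.5, 0.8 or 0.9. So with complete data the internal rule is blunt for moderate errors but not inert. A gross error drives the estimated between-participant variance to about zero, and the residual then approaches 3.16.

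**What a flag changes.** It opens optional analyses with other transformations or with outliers excluded. SAP 5.1 has no hypothesis test and no decision rule. The planned model, its estimates and its intervals are the same with or without a flag.

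**The case for a change.** The best case for a change is that the fix costs one clause and the other safeguards are incomplete. The residual plots are kept out of the study report, so a reader cannot check the visual judgement. The mandatory exclusion in SAP 5.3.1 covers only plasma parameters already known to be biased, while Fa rests on urine totals. The other exclusions in SAP 5.3 are discretionary. Choosing the residual type after seeing six participants' data would be post hoc.

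The omission and the ceilings stand. The consequence does not follow, for three reasons.

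- The number is not the only trigger. Major departures from normality, judged from the plots, lead to the same follow-up, so an isolated residual of 2.8 can be acted on even where 3 is unreachable.
- A discrepant participant is visible elsewhere. Individual F and Fa are listed, and box plots show the values behind both (SAP 6.2.2 and 6.2.3). Terminal-phase fit and percent extrapolated AUC are listed, and each participant's dose-normalized oral and IV Period 2 profiles are overlaid (SAP 6.2.1).
- The alternatives are not clearly better. External residuals with a cut-off of 3 flag about 5-15% of clean datasets and still miss 7-49% of 3-fold errors at six pairs. If variances are re-estimated at each deletion, the conditional form flags 27-34% of clean datasets. With N = 11, a 3-fold error in the unpaired value is caught in only about 3-25%. A Bonferroni limit on six log-ratios (4.85) catches 31% at within-participant log-SD 0.2.

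With six participants, a conservative trigger for setting data aside is defensible. A leave-one-out range reported regardless of any flag would be a new output, not the repair of an error.

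**Conclusion.** No change is needed. SAP 5.2.3 leaves a software detail unstated. Under one reading its cut-off is insensitive to moderate errors with 12 values and unreachable with 11 or 10. Those ceilings are exact; the detection rates rest on assumed log-SDs because the documents give none. The gap has no effect on what the trial reports as planned: F and Fa are secondary, nothing is tested, a flag only permits optional analyses that must be justified, and the plots and listings do not depend on the cut-off. An analyst who states the residual type when running the check fills the gap sensibly.

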5.3. Methods to Manage Missing Data

For the analysis of safety endpoints, the sponsor data standard rules for imputation will be applied.

In all PK data presentations (except listings), concentrations below the limit of quantification (BLQ) will be set to zero. In listings BLQ values will be reported as “<LLQ”, where LLQ will be replaced with the value for the lower limit of quantification.

In PK summary tables and plots of median profiles, statistics will be calculated having set concentrations to missing if one of the following cases is true:

1. A concentration has been collected as ND (i.e. not done) or NS (i.e. no sample),
2. A deviation in sampling time is of sufficient concern or a concentration has been flagged anomalous by the pharmacokineticist.

Note that summary statistics will not be presented at a particular time point if more than 50% of the data are missing.

Participants who experience events that may affect their PK profile (e.g. lack of compliance with dosing or vomiting) may be excluded from the PK analysis. At the discretion of the pharmacokineticist a concentration value may also be excluded if the deviation in sampling time is of sufficient concern or if the concentration is anomalous for any other reason.

A full list of protocol deviations will be compiled and reviewed to identify major and minor deviations prior to database closure.

5.3.1. Plasma Pharmacokinetic Parameters

Actual PK sampling times will be used in the derivation of plasma PK parameters.

If a PK parameter cannot be derived from a participant's concentration data, the parameter will be coded as NC (i.e. not calculated). (Note that NC values will not be generated beyond the day that a participant discontinues.)

In summary tables, statistics will be calculated by setting NC values to missing; and statistics will be presented for a particular treatment group/analyte with ≥ 3 evaluable measurements.

Note: If $N < 3$ evaluable measurements, only mean, median and range will be provided in summary statistics.

For statistical analyses (i.e. mixed effect model), PK parameters coded as NC will also be set to missing; and analyses will not be performed for a particular parameter if more than 50% of the data are NC.

If an individual participant has a known biased estimate of a plasma PK parameter (due for example to an unexpected event such as vomiting before all the compound is adequately

absorbed in the body), this will be footnoted in summary tables and will not be included in the calculation of summary statistics or statistical analyses.

6. ANALYSES AND SUMMARIES

6.1. Primary Endpoint(s)

6.1.1. Extent of Excretion (Period 1 Only)

Radioactivity excreted in urine and/or feces will be reported as the percentage of the administered radioactivity excreted at each time interval, cumulatively through that interval and the total percent of dose recovered in urine, feces, and/or emesis (if any).

Percent recovery and cumulative recovery of total radioactivity in urine, feces and emesis (if any) will be determined based on total administered dose.

Note: While the total percentage of dose excreted is the primary endpoint, the percentage of the administered radioactivity excreted at each time interval and cumulatively through that interval are tertiary endpoints.

*Individual participant and median data profiles for total radioactivity will be graphically presented for the cumulative recovery of radioactivity in urine, feces and their combination in **Period 1 only**. Emesis, if any, will be collected during 24 hours post oral dose, but these participants will not necessarily be excluded from analysis. The total recovery of radioactivity in urine, feces (and emesis, if any) and their combination will be listed and summarized for **Period 1 only**.*

Primary results of the extent of excretion (i.e., radioactivity in urine, feces, and vomitus if observed) will be detailed in a separate report provided by ICON and will be summarized within the CSR.

6.1.2. Metabolic Profiling and Metabolite Identification

Results of the metabolic profiling analysis will be detailed in a separate report and will be summarized within the CSR.

6.2. Secondary Endpoint(s)

6.2.1. Plasma PK parameters of PF-07081532 and total radioactivity in Period 1 and [¹⁴C]PF-07081532 in Period 2

Plasma PK parameters of PF-07081532 (Period 1), total radioactivity (Period 1) and [¹⁴C]PF-07081532(Period 2), as described in [Section 3.2.1](#), will be listed and summarized descriptively by analyte, route of administration (IV vs. Oral) and treatment for participants in the PK analysis set (as defined in [Section 4](#)) using nominal sampling times. Missing values will be handled as detailed in [Section 5.3](#).

The relevant plasma PK parameters for each analyte, route of administration and treatment (see [Section 3](#)) will be summarized as specified in the table below:

Table 3. Summary statistics to be produced for Plasma PK Parameters

Parameter	Summary Statistics
AUC1ast, AUCinf, AUC1ast(dn), AUCini(dn), Cmax, Cmax(dn), MRT, CL/F (oral), Vz/F (oral), CL (IV) and Vss(IV)	N, arithmetic mean, median, cv%, standard deviation, minimum, maximum, geometric mean and geometric cv%.
Tmax	N, median, minimum, maximum.
t _{1/2}	N, arithmetic mean, median, cv%, standard deviation, minimum, maximum.

Box and whisker plots for individual participant parameters (AUCinf(dn), AUClast(dn), and Cmax(dn) be presented and overlaid with geometric means.

Supporting data from the estimation of *t*_{1/2} and AUCinf will be listed by analyte: terminal phase rate constant (ke1); goodness of fit statistic from the log-linear regression (i2); the percent of AUCinf based on extrapolation (AUCextrap%); and the first, last, and number of time points used in the estimation of ke1. These data may be included in the clinical study report.

The following summaries will additionally be presented for the plasma concentration data of the analytes using the PK Concentration Set (as defined in [Section 4](#)):

- a listing of all concentrations sorted by participant ID and nominal time post-dose for each analyte, route of administration and treatment, separately. The concentration listing will also include the actual times. Deviations from the nominal time will be given in a separate listing.
- a summary of concentrations by each nominal time post-dose (produced separately for each analyte), where the set of statistics will include n, mean, median, standard deviation, coefficient of variation (cv), minimum, maximum and the number of concentrations above the lower limit of quantification.
- median concentration time plots (on both linear and semi-log scales) against nominal time post-dose by analyte for PF-07081532 (Period 1) and total radioactivity (Period 1) only. The concentration time plots for these analytes will be presented together on the same plot.
- median concentration time plots (on both linear and semi-log scales) against nominal time post-dose by analyte and route of administration for PF-07081532 (Period 2) and [¹⁴C]PF-07081532 (Period 2) only, where both have been dose-normalized (by oral and IV dose, respectively). The dose-normalization will be calculated by programming using raw concentrations and the actual doses administered. The concentration time plots for these analytes will be presented together on the same plot.
- individual concentration time plots by analyte (on both linear and semi-log scales) against actual time post-dose (there will be separate spaghetti plots for each analyte per scale).
- individual concentration time plots by participant (on both linear and semi-log scales) against a

-07081532

PFIZER CONFIDENTIAL

(Period 1) and total radioactivity (Period 1) will be presented together on the same plot. In a separate figure, the analytes PF-07081532 (Period 2) and [¹⁴C]PF-07081532 (Period 2), where both have been dose-normalized (by programming using raw concentrations and the actual doses administered), will be presented together on the same plot.

The nominal PK sampling time will be used for summary statistics and relevant median plots, whereas for individual participant plots by time, the actual PK sampling time will be used.

